4.3.1 Incomplete Dates for Concomitant Medication and Adverse Events

For analyses of AEs and concomitant medication usage, a complete date must be established in order to correctly identify the AE or medication as occurring during treatment or not. For purposes of imputing missing components of partially-reported start and stop dates for AEs and for medication use, the algorithms listed below will be followed. Start and stop dates of AEs or concomitant medication will be displayed as reported in the subject data listings (ie, no imputed values will be displayed in data listings).

Missing start day, but month and year present:

- If the occurrence of the AE/concomitant medication is in the same month and year as is the date of first dose of investigational product in Period II (which is the first Two-Week Double-Blind Treatment Period), then the start day of the event/concomitant medication will be assigned to the day of the first dose of investigational product taken in Period II.
- If the occurrence of the AE/concomitant medication is in the same month and year as is the date of the first dose of investigational product in period IV (which is the second Two-Week Double-Blind Treatment Period), then the start day of the event/concomitant medication will be assigned to the day of the first dose of investigational product taken in Period IV.
- If the dates of first dose of investigational product for Period II and for Period IV fall in the same month, then the start date day of the event/concomitant medication will be assigned to the day of the first dose of investigational product taken in Period II.
- Otherwise, the start day will be set to the 1st day of the month.

Missing start day and month, but year present:

- If the occurrence of the AE/concomitant medication is in the same year as is the date of first dose of investigational product in Period II (which is the first Two-Week Double-Blind Treatment Period), then the start day of the event/concomitant medication will be assigned to the day of the first dose of investigational product taken in Period II.
- If the occurrence of the AE/concomitant medication is in the same year as is the date of the first dose of investigational product in period IV (which is the second Two-Week

Double-Blind Treatment Period), then the start day of the event/concomitant medication will be assigned to the day of the first dose of investigational product taken in Period IV.

- If the dates of first dose of investigational product for Period II and for Period IV fall in the same year, then the start date day of the event/concomitant medication will be assigned to the day of the first dose of investigational product taken in Period II.
- Otherwise the start day and month will be set to January 1st.

Missing end day, but month and year present:

- The end day will be set to the last day of the month.

Missing end day and month, but year present:

- The end day and month will be set to the maximum of the date of study termination or the date equivalent to 30 days after the last dose of the double-blinded medication.
- However, if the study termination year and year for the date of the last dose of the double-blinded medication +30 days are greater than the event/concomitant medication year, the day and month are to be set to December 31st.

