1.1 Study Design

This is a multi-center, double-blind, randomized, placebo-controlled, crossover study in dementia subjects with gait impairment. The primary objective of the study will be to evaluate the effect of intepirdine on gait speed. The secondary objective is to assess the safety and tolerability of intepirdine. Exploratory objectives of the study include the evaluation of the effects of RVT-101 on other quantitative and qualitative measures of gait and balance.

Following an initial screening period, eligible subjects will enter a two-week single-blind placebo run-in period (Period I). At the end of this period, all subjects who continue to meet the eligibility criteria will enter the first two-week double-blind treatment period (Period II). Following the completion of Period II, subjects will undergo a washout period (Period III) of two weeks during which subjects will receive placebo. After the two-week washout, subjects will enter the second two-week double-blind treatment period (Period IV). A safety follow-up telephone call will be conducted approximately 2 weeks after completion of Period IV.

Figure 1 provides a study scheme demonstrating the key design elements and scheduled study visits.

Figure 1. Study Design

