7.1 Adverse Events

Adverse events will be classified using the MedDRA version 18.1 coding dictionary. Tabulations will include an overall incidence of at least one adverse event, incidence within system organ class (SOC), and incidence by preferred term. Each subject may only contribute once per treatment group, that is by first occurrence to each of the incidence rates, regardless of the number of occurrences, as follows:

- Adverse events occurring prior to the first dose of double-blind investigational product will be referred to as Treatment-Emergent AEs (TEAEs) and presented as Placebo Run-In events.
- Adverse events occurring on or after the first dose of each double-blind two-week treatment period (Period II and period IV), and within 7 days of the last dose of double-blind investigational product, will be referred to as TEAEs and presented by treatment group.
- Events occurring 7 days after the last dose of Period II and Period IV and for the post-treatment Follow-up Period starting at day 8 (up to 14 days post-last-dose) will be presented as Post-Treatment Period. These events will only be included in a data listing.

Tabulations of the incidence of AEs will be presented as follows:

- Overview of TEAE
- TEAE by SOC and preferred term
- TEAE by preferred term
- TEAE by SOC, preferred term, and relationship to study drug
- TEAE by SOC, preferred term, and maximum severity (mild, moderate, and severe)

All AEs will be listed with its relationship to study drug and severity, flagging those which are not events during treatment-emergent period.

A listing of all deaths and serious AEs will be provided. Any TEAE leading to study drug temporary and permanent discontinuation will also be listed.

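### SAP 4.3.1 can date a Period II adverse event to the first Period IV dose, under the opposite treatment, even when its recorded stop date shows it had already ended

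*SAP*

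**What the plan says.** SAP 4.3.1 gives the purpose of the imputation: "a complete date must be established in order to correctly identify the AE or medication as occurring during treatment or not". For a start with month and year known and day missing, it has four bullets:

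1. If the month is that of the first Period II dose, the start "will be assigned to the day of the first dose of investigational product taken in Period II".
2. If the month is that of the first Period IV dose, the start "will be assigned to the day of the first dose of investigational product taken in Period IV".
3. "If the dates of first dose of investigational product for Period II and for Period IV fall in the same month", the first Period II dose is used.
4. Otherwise, the 1st of the month is used.

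The end-date rule stands apart. If the end day is missing, "The end day will be set to the last day of the month". No bullet compares an imputed start with a reported stop date.

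Under SAP 7.1, events from the first dose of each double-blind period and "within 7 days of the last dose of double-blind investigational product, will be referred to as TEAEs and presented by treatment group". Events before the first double-blind dose are shown as Placebo Run-In events. Under SAP 1.4, Periods II and IV carry opposite treatments in both sequences.

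**The concern.** In a parallel-group trial, dating an uncertain onset to the first dose still counts the event on the subject's only treatment. In this crossover, bullet 2 can take an event from one treatment and give it to the other. In sequence AB an intepirdine event becomes a placebo event, and in BA the reverse, so any true difference in event rates is diluted.

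The result can also be impossible on the subject's own record, because nothing stops the imputed start from falling after the recorded stop. It departs from protocol 10.4.1.1 as well, which attributes an event to the treatment last received: an event that ended before the first Period IV dose cannot belong to Period IV. SAP 4.2 gives the SAP precedence, so the month rule would govern.

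Safety and tolerability is the only secondary objective, in about 30-40 subjects. A few moved events would be visible in the by-treatment tables.

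**Working it through.** The documents give no figure on this point, so there is none to reproduce. The check applies the four bullets to every possible case.

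**Inputs.** Period II lasts two weeks (14 dosing days), and then "Following the completion of Period II, subjects will undergo a washout period (Period III) of two weeks" (SAP 1.1). The first Period IV dose is therefore nominally 14 + 14 = 28 days after the first Period II dose. The attribution tail is 7 days (SAP 7.1). Visits may move by 3 days either way and are re-based on the previous visit (protocol 8.1), so the gap between first doses runs from 11 + 11 = 22 to 17 + 17 = 34 days. Assumptions: Period II start dates are uniform over a 365-day year, onset is uniform within the period, and only the start day is missing.

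**Example where the rule fails.** First doses are 25 March and 22 April. An event runs from 2 to 5 April, within Period II, and its start day is not recorded. April is not the month of the first Period II dose, but it is the month of the first Period IV dose, so bullet 2 gives 22 April. That is 22 - 5 = 17 days after the event ended, and under the other treatment.

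**Example where it does not.** First doses are 2 and 30 March. An event on 6 March is dated 2 March under bullet 3 and stays in Period II.

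**Share moved, nominal schedule.** For a window of L onset days, each of the 12 month-ends pushes L(L-1)/2 onset days into the next month. With a 28-day gap Period IV always starts in that month, so all of them go to Period IV. The share is 12 × L(L-1)/2 ÷ (365 × L) = 6(L-1)/365.

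- Period II dosing days, L = 14: 6 × 13/365 = 21.4% (1092 of 5110).
- Period II plus 7 days, L = 21: 6 × 20/365 = 32.9% (2520 of 7665).

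Of the 1498 Period II onset days that fall in the month Period IV starts, 1092 (72.9%) are moved. The other 406 (27.1%) stay in Period II because of bullet 3.

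**Other schedules.** Direct enumeration, with the figure including the 7-day tail in brackets:

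| Period II length | Gap between first doses | Moved to Period IV |
|---|---|---|
| 14 days | 22 days | 21.4% (32.9%) |
| 14 days | 28 days | 21.4% (32.9%) |
| 14 days | 34 days | 11.6% (22.4%) |
| 11 days | 22 days (11 + 11) | 16.4% (27.9%) |
| 17 days | 34 days (17 + 17) | 16.2% (27.2%) |
| 17 days | 28 days (17 + 11) | 26.3% (37.8%) |

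The first and third rows vary the gap alone. Strictly, a 14-day Period II allows only 14 + 11 = 25 to 14 + 17 = 31 days. Over all combinations inside the visit windows, the range is 16.2% to 26.3% (27.2% to 37.8%).

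**Error in the other direction.** When both first doses fall in one month, Period IV events in that month go to Period II. At 28 days this needs a Period II start on day 1 to 3 of a 31-day month (3 + 2 + 1 = 6 Period IV days) or day 1 to 2 of a 30-day month (2 + 1 = 3). That is 7 × 6 + 4 × 3 = 54 of 5110 Period IV days, or 1.1%. At 22 days it is 480 of 5110, or 9.4%. At 34 days it is nil.

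**Run-in events under bullet 1.** With a 14-day run-in, 105 run-in days per month-end fall in the month before the first Period II dose. The other 5110 - 12 × 105 = 3850 of 5110 (75%) share its month and are dated to that dose. Where a stop date shows that such an event ended earlier, SAP 7.1 would place it in the Placebo Run-In.

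**The case against.** A reader might infer that an event moves whenever its month is the one in which Period IV starts. The documents do not support that: bullet 3 keeps it in Period II when both first doses share the month. The defect needs Period II to have started in an earlier month.

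A reader might also infer that the rule will hide a tolerability signal. Nothing in the documents allows that to be sized. The percentages apply only to events with a missing start day, and that share is not given. It may be small: a regular caregiver attends visits and reports on the subject (protocol 6.2, criterion 12), events are reviewed about every 14 days, and source records must hold start and end dates (protocol 11.1.5). The safety analysis is descriptive. All events are listed with dates as reported, so a misplaced event could be traced, although the listing would not show the imputed date behind the table.

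Bullet 1 is milder. Counting an uncertain run-in event as on treatment is a familiar cautious convention, and it does not take the event from one double-blind treatment and give it to the other. That defence holds where the timing is uncertain. It fails where the stop date shows that the event ended before the first double-blind dose.

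These points limit how often the rule does harm. They do not justify a start date later than the recorded stop.

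**Conclusion.** The rule is wrong as written, in a defined set of cases: start day missing, Period II begun in an earlier month than Period IV, and onset in Period II or its 7-day tail but in the month of the first Period IV dose. Such an event is credited to the opposite treatment. If it has a recorded stop before that dose, the error is provable from the subject's own data.

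Conditional on a missing start day, about one in five Period II onset days is affected at the nominal schedule, and one in three with the tail. These shares rest on uniform start dates and onsets. They count all exposed onset days, not only those with a stop date early enough to reveal the error. The unconditional effect on the tables cannot be stated. The correction is worth making before database lock because it is cheap and the present text can yield impossible dates.

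**What to change.** Add to SAP 4.3.1:

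- An imputed start may not be later than the recorded stop date. Apply this to concomitant medications too.
- Where the stop date precedes the first dose that a bullet would assign, place the event in the period (run-in, Period II plus 7 days, or washout) consistent with the reported month and the stop date. If that leaves both Period II plus 7 days and washout open, state the choice in advance; the cap still applies.
- If the visit of first recording is available, also require the start to be no later than that visit and after the previous adverse event review visit. Events first recorded at Visit 6 then stay in Period IV.
- Otherwise keep the existing bullets.

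Do not add a general default to the earlier double-blind period. A stop date and a first-recording date are both upper limits on onset, so neither can rule out Period II for a true Period IV event. Enumerated with a 14-day Period II plus 7 days, such a default would send 52% of Period IV onsets with a missing start day to Period II at a 28-day gap (2674 of 5110). The figures are 72% at 22 days and 33% at 34 days, against 1.1% at 28 days under the present rule.

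The cost is a few lines of SAP text and programming. The stop-date cap cannot help where the stop date is missing or late. The visit-based limit depends on a field for the visit of first recording, which the documents do not show is collected.

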4.3.2 Missing Walkway Data

No values will be imputed for missing data. If one of the triplicate measurements for a Gait parameter are missed, the average of the remaining two measurements can be used in the analyses. If two of or all the triplicate measurements are missing at a timepoint for a Gait parameter, no values will be imputed or calculated for this timepoint.

4.3.3 Missing MDS-UPDRS Data

MDS-UPDRS items with missing responses will be recoded with imputed values. The imputation approach used for each missing item within a scale will be mean item substitution, such that the missing item response will be recoded as the mean of the subjects' numeric responses to all non-missing items on the same scale (ie, Part II or Part III) at the same assessment.

According to a recent report by Goetz et al. (2015), values for missing items within a scale will only be imputed at assessments for which the number of missing items on the scale comprise ≤ 2 items for Part II, and ≤ 7 items for Part III. If a value for a missing item cannot be computed, then no scale or composite score which includes that item can be calculated.

No separate imputations for missing values will be conducted for items specific to the PIGD 4-item and MDS-UPDRS 7-item subscales. These subscales will be scored only if values are available for all the corresponding Part III items.

4.3.4 Missing Baseline Data

For efficacy evaluations, the baseline is considered invalid and will be excluded from the analysis if an assessment being analyzed is completed after the first dose of double-blind investigational product has been taken.

To assess sensitivity to missing data assumptions, the primary analysis of gait speed will be repeated with above invalid baseline included or substituting them with the respective non-missing assessment at Visit 2.

4.4 Subgroups

The efficacy and safety analyses will also be presented by the following subgroups:

- Dementia type (AD, LBD)
- Baseline MMSE (14-19, 20-26)
- Sex (Male, Female) [Note: efficacy analysis only]

5 BASELINE AND OTHER SUMMARIES AND ANALYSES

5.1 Subjects Disposition

The total number of subjects that participated in the study will be summarized, including whether they were randomized or not. A tabulation will be provided for the number of subjects screened and screen-failed prior to the Placebo Run-in period. The denominator for those outcomes for this analysis will be based on the number of screened subjects.

The number of subjects entering the Placebo Run-in and the number of subjects not completing the Placebo Run-in (and reasons for not completing) will be presented, using the subjects entering the Placebo Run-in as the denominator.

The number of subjects randomized, as well as the number of subjects in the analysis populations (Safety, ITT, Per Protocol, Completers populations), will be presented for the Randomized Population. This will be summarized by sequence.

An overall summary of the number and percentage of subjects who completed or withdrew prematurely from the study will be displayed by sequence, for the overall population as well as by dementia type (AD versus LBD [DLB and PDD]) strata. Reasons for premature withdrawal will be presented in the order they are displayed in the CRF. Subjects who withdrew prematurely from the study will be listed by treatment group and subject.

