#### **10.4.1.1. Adverse Events**

AE verbatim text will be coded and classified by body system and preferred (coded) term using the Medical Dictionary for Regulatory Activities (MedDRA). AEs will be assigned to the treatment based on the last dose received. All AEs will be listed. AEs, Drug related AEs, SAEs, AEs that lead to discontinuation of investigational product will be summarized by treatment group. AEs will be summarized separately for the Single-Blind Run-In Period, the Double-Blind cross-over Treatment Period and the Follow-up Period.

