4.1.5 Visits and Periods

There are 5 study periods during this study:

- The Screening Period is defined as the period of time prior to the subject receiving the first dose of single-blind placebo run-in medication.
- The Single-Blind Placebo Run-In Period (Period I) is defined as the period from the first dose of single-blind run-in medication and ends on the last dose date of single-blind run-in medication. The assessments taken on the date of the first dose of randomized double-blind investigational product will be assumed to have been completed before the first dose of double-blind investigational product and will be slotted to this period.
- The First Two-Week Double-Blind Treatment Period (Period II) starts on the date of first dose of double-blind investigational product and ends on the last dose date. If the first dose of randomized investigational product is taken on the same day as Visit 3 assessments, it will be assumed that the assessments were completed before the first dose of double-blind investigational product has been taken.
- The Single-Blind Placebo Washout Period (Period III) starts one day after the last dose of the double-blind medication has been taken in Period II and lasts until the first dose of the double-blind investigational product in Period IV. The assessments taken on the date of the first dose of randomized double-blind investigational product will be assumed to have been completed before the first dose of double-blind investigational product and will be slotted to this period.
- The Second Two-Week Double-Blind Treatment Period (Period IV) starts on the date of the first dose of double-blind investigational product and ends on the last dose date. If the first dose of randomized investigational product is taken on the same day as Visit 5 assessments, it will be assumed that the assessments were completed before the first dose of double-blind investigational product has been taken.

A safety follow-up telephone call will be conducted approximately 2 weeks after completion of Period IV.

Study visits will be determined from the scheduled times as reported on the CRF. As indicated in Table 1, Schedule of Assessments visit windows of +/- 3 days are allowed for scheduling purposes. For analysis purposes in this crossover study, no visit reassignment will be used even if a visit falls before or after the scheduling window.

Table 1: Schedule of Events

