7.6 Suicidality

The following outcomes are C-SSRS categories and have binary responses (yes/no). The categories have been re-ordered from the actual scale to facilitate the definitions of the composite and comparative endpoints, and to enable clarity in the presentation of the results.

- Category 1 – Wish to be Dead
- Category 2 – Non-specific Active Suicidal Thoughts
- Category 3 – Active Suicidal Ideation with Any Methods (Not Plan) without Intent to Act
- Category 4 – Active Suicidal Ideation with Some Intent to Act, without Specific Plan
- Category 5 – Active Suicidal Ideation with Specific Plan and Intent
- Category 6 – Preparatory Acts or Behavior
- Category 7 – Aborted Attempt
- Category 8 – Interrupted Attempt
- Category 9 – Actual Attempt (non-fatal)
- Category 10 – Completed Suicide
- Self-injurious behavior without suicidal intent is also a C-SSRS outcome (although not suicide-related) and has a binary response (yes/no)

Endpoints based on the above categories are defined below.

- Suicidal ideation: A “yes” answer at any time during treatment to any one of the five suicidal ideation questions (Categories 1-5) on the C-SSRS
- Suicidal behavior: A “yes” answer at any time during treatment to any one of the five suicidal behavior questions (Categories 6-10) on the C-SSRS
- Suicidal ideation or behavior: A “yes” answer at any time during treatment to any one of the ten suicidal ideation and behavior questions (Categories 1-10) on the C-SSRS
- Self-injurious behavior without suicidal intent: a binary response (yes/no)

The number and percentage of subjects with any occurring suicidal events (ideation or behavior) will be presented by treatment group and time point.

A listing of all C-SSRS data will be provided, while a listing of subjects who demonstrated a worsening on any one of the four endpoints will also be provided for pre-and post-treatment (V3 vs V4 and V5 vs V6) including the Day on Treatment the C-SSRS was collected.

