9 CHANGES FROM THE PROTOCOL TO THIS SAP

There are no meaningful changes from the protocol to this SAP. Additional details and specifications have been included in this SAP to allow for better understanding of the intended procedures.

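### SAP 5.1 counts withdrawals only by crossover sequence, and SAP 7.1 names only listings where the protocol promises by-treatment summaries of AEs leading to discontinuation and of SAEs; Section 9 does not declare the change

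*SAP*

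**What the plan says.** **Withdrawals.** SAP 5.1 plans one tabulation of completion and withdrawal for randomized subjects: "An overall summary of the number and percentage of subjects who completed or withdrew prematurely from the study will be displayed by sequence". It is shown overall and by dementia type. A listing follows: "Subjects who withdrew prematurely from the study will be listed by treatment group and subject". No rule says which treatment group a subject belongs to who stops during the placebo washout.

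**AEs leading to discontinuation, and SAEs.** Protocol 10.4.1.1 commits to summaries: "AEs, Drug related AEs, SAEs, AEs that lead to discontinuation of investigational product will be summarized by treatment group". SAP 7.1 names five TEAE tabulations: an overview, SOC with preferred term, preferred term alone, relationship and maximum severity. Neither discontinuations nor SAEs is among them. They appear as listings: "Any TEAE leading to study drug temporary and permanent discontinuation will also be listed" and "A listing of all deaths and serious AEs will be provided".

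**Status of the difference.** SAP 4.2 gives the SAP precedence where it differs from the protocol. Section 9 says: "There are no meaningful changes from the protocol to this SAP".

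**Related outputs.** SAP 5.8 tabulates double-blind exposure by treatment group in three categories: up to 1 week, over 1 to 2 weeks, and over 2 weeks. SAP 1 places the table specifications in a separate spreadsheet, which is not part of these documents.

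**The concern.** Safety and tolerability is the trial's only secondary objective. Under Protocol 6.6.1 a subject who permanently stops investigational product counts as withdrawn from the study, so withdrawal by treatment is a direct measure of tolerability. A sequence label does not carry that information. An AB withdrawal may have happened on intepirdine, on washout placebo or on double-blind placebo, and the same is true for BA. If intepirdine caused most of the stops, the planned table would be expected to look balanced.

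The protocol's by-treatment summary of AEs leading to discontinuation would partly make up for this, but the SAP does not name it. A reader who relies on Section 9 would not know that it, or the SAE summary, had become a listing.

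**Working it through.** The plan has no figure of its own to reproduce. SAP 1.3 reports no power calculation, and the documents give no dropout rate. The rates and counts below are assumptions. The allocation (1:1) and the size (about 30-40, so about 15-20 per sequence) come from SAP 1.3 and 1.4.

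**1. Expected withdrawals by sequence.** Let pd be the withdrawal risk in a period on intepirdine and pp the risk in a period on placebo. Assume no period effect and ignore washout.

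- AB: pd + (1 - pd)*pp = pd + pp - pd*pp
- BA: pp + (1 - pp)*pd = pd + pp - pd*pp

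The two are equal whatever the drug does. With assumed pd = 0.15, pp = 0.05 and 18 per sequence:

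- AB: 0.15 + 0.85*0.05 = 0.1925
- BA: 0.05 + 0.95*0.15 = 0.1925
- Expected withdrawals: 18*0.1925 = 3.47 in each sequence

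Counted by treatment, the same example separates:

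- Intepirdine: 18 + 18*0.95 = 35.1 subjects dosed, 35.1*0.15 = 5.3 withdrawals
- Placebo: 18 + 18*0.85 = 33.3 subjects dosed, 33.3*0.05 = 1.7 withdrawals

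**2. Counting check.** Suppose equal numbers withdraw in each sequence, either all on intepirdine or all on placebo. A subject who stops in Period II never takes the second treatment, which sets the denominators.

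| Per sequence | By-sequence table | All stops on intepirdine | All stops on placebo | Fisher p |
|---|---|---|---|---|
| 20, with 4 withdrawn | 4/20 and 4/20 | intepirdine 8/40, placebo 0/36 | intepirdine 0/36, placebo 8/40 | 0.006 |
| 15, with 3 withdrawn | 3/15 and 3/15 | intepirdine 6/30, placebo 0/27 | intepirdine 0/27, placebo 6/30 | 0.02 |

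The p-values ignore the within-subject pairing and are for illustration only. The by-sequence table is identical in two opposite situations.

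**3. What the exposure table recovers.** It shows stops in the first week by treatment. Through the numbers exposed (36 against 40 in the first row), it also reflects subjects who never reached Period IV. But Protocol 8.1 allows 3 days either side of a visit, so a completer can have 11 to 14 days of exposure. That falls in the same category as a stop at day 8-10. The table also leaves out interruption days and gives no reasons.

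**4. Washout.** SAP 7.1 counts events up to 7 days after the last double-blind dose as TEAEs. Events from washout day 8 are post-treatment and go to a data listing only. An AE starting then and leading to withdrawal is therefore outside the listing of TEAEs leading to discontinuation. Protocol 10.4.1.1 instead assigns AEs by last dose received, which in washout, read literally, is placebo. An event on washout day 3 after intepirdine would go to placebo under that reading and to intepirdine under the SAP.

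**The case against.** The strongest reply is that the information is still there. Withdrawn subjects are listed by treatment group, and with 30-40 subjects a reader can count them. Exposure is tabulated by treatment. All AEs are listed, with those outside the treatment-emergent period flagged, and the death and SAE listing is not limited to TEAEs. The TEAE overview has undefined rows, and the separate spreadsheet might include a discontinuation row. The protocol never promised a disposition table by treatment, and disposition by randomized sequence is ordinary accounting.

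Much of this stands. A reader might infer that no planned output can show whether subjects stop more often on intepirdine. The documents do not support that, because the listings and the exposure table carry part of the answer, and the overview can be neither credited nor ruled out. What remains is that a listing gives no rate or denominator. Without a rule for washout withdrawals, two readers could also count it differently.

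A reader might also infer that suicidality data are lost for subjects who stop mid-period. The worsening listing "will also be provided for pre-and post-treatment (V3 vs V4 and V5 vs V6" does not name the ET visit. But SAP 7.6 also tabulates suicidal events by treatment group and time point, defines its endpoints over any time during treatment, and lists all C-SSRS data. The rule in SAP 4.1.5 that "no visit reassignment will be used even if a visit falls before or after the scheduling window" concerns visits outside their window and does not address how ET data are used. At most, one supplementary listing needs a clarifying line.

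Finally, attributing every washout-onset event to the preceding double-blind treatment would not restore the protocol, whose rule is the last dose received. Such events should be shown separately.

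**Conclusion.** The point holds in two parts. First, the only withdrawal table that the SAP names cannot identify the treatment at withdrawal. That follows from the design. The exact equality of expected proportions also needs no period effect and no washout withdrawals, and observed counts in about 15-20 subjects per sequence can differ by chance. The 15% and 5% risks are illustrative. Second, two by-treatment summaries promised in Protocol 10.4.1.1 are named in the SAP only as listings, and Section 9 does not declare this.

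The consequence is limited to reporting of the secondary objective. The primary gait-speed analysis is not affected, and no collected data are lost. It should still be corrected, because it is an undeclared difference from the protocol on tolerability and is simple to repair.

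**What to change.** - **SAP 5.1:** add a table of premature withdrawals and reasons by period and treatment at withdrawal. The denominator is subjects dosed on that treatment in that period. Show washout withdrawals in separate rows by preceding double-blind treatment. Keep the by-sequence table for accounting.
- **SAP 7.1:** restore the by-treatment summaries of AEs leading to discontinuation and of SAEs. Extend the discontinuation listing to events starting from washout day 8, shown separately by preceding treatment. Reconcile the protocol's last-dose rule with the SAP's 7-day rule and state one attribution rule.
- **SAP 7.6 (optional):** state that the worsening listing uses the ET C-SSRS against that period's baseline when V4 or V6 is absent.
- **SAP 9:** declare any difference from the protocol that remains.

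The cost is SAP wording and a few small tables programmed from data already collected. Trial conduct does not change.
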